#### **Statistical Approach & Data Analysis:**

**Preliminary Analysis:** Descriptive analyses will include comparison of the baseline characteristics of participants in the two treatment arms. Continuous variables will be summarized using means, medians, and standard deviations. Categorical variables will be presented as frequencies. Continuous variables that are normally distributed will be analyzed with Students T-test, and for those that are not normally distributed nonparametric tests will be used. Chi-square and Fisher's exact will be used to analyze ordinal variables.

**Primary Aim:** Observed pregnancies in the LNG-IUS group will be compared to those in the oral group. Because our primary outcome, pregnancy rate (yes/no) is a dichotomous variable, logistic regression will be used.

**Secondary Aim1:** One secondary aim is to evaluate long-acting reversible contraception (LARC) use at 6 and 12months. We hypothesize that women randomized to the LNG-IUS group will be more likely to be using a LARC method. This categorical variable (yes/no use) will be presented as frequency of LARC use in the two groups. Chi-square and logistic regression will be used for analysis.

**Secondary Aim2:** Continuation and satisfaction in LNG-IUS arm will be evaluated. Both continuation and satisfaction will be assessed as dichotomous variables. Continuation and satisfaction (satisfied/ not satisfied) will be presented as frequencies and analyzed with Chi-square and logistic regression.

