## INNOVATION:

There are currently no data addressing the use or effectiveness of the LNG-IUS as a method of emergency contraception. This proposal will provide essential information to both patients and clinicians in this field. Specifically, the LIFE study (levonorgestrel IUS For Emergency contraception) will answer the following questions:

- 1) Is the LNG-IUS an effective method of emergency contraception?
- 2) Is the LNG-IUS more effective than the oral levonorgestrel regimen?
- 3) Are women receiving LNG-IUS more likely to be using a LARC method at 6 months?
- 4) Are women receiving the LNG-IUS as emergency contraception still using and satisfied with their method at 6 months and at 12 months?

Current practices in the United States provide women 4 choices of EC. A modified regimen of combined oral contraceptives (Yuzpe method) has been shown to be the least effective and associated with the most side-effects. There are two additional oral regimens, the levonorgestrel and ulipristal acetate regimens which are effective for a single act of unprotected intercourse. The most commonly-used method is the oral levonorgestrel regimen which is largely available over the counter. Ulipristal acetate is the newest regimen, approved by the FDA in August 2010, requires a physician prescription, and is more expensive than the levonorgestrel option. The most effective, least used and most expensive method of EC is the Cu-T380. This method, unlike the previous methods, provides continued highly effective long-term contraception. The levonorgestrel-IUS is the only other intrauterine device available in the U.S. The LNG-IUS is currently used only for standard contraception, not emergency contraception. In this setting it has been shown to be highly effective, convenient, forgettable, cost-effective, and extremely well-liked by users. *This research is innovative, because we will be evaluating a new method of emergency contraception and expanding access to include a well-liked, long-term, and extremely effective method of contraception that has the potential to reduce unintended pregnancy and abortion rates.* The American College of Obstetricians and Gynecologists Committee on Gynecologic Practice Opinion, published in 2009 suggested that the high rates of unintended pregnancy may be a direct consequence of low use of long acting reversible contraceptives.

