**Secondary Aim 2:** One secondary aim of this project is to quantify the contraceptive continuation and satisfaction rates of the participants randomized to LNG-IUS. The objective of this aim is to demonstrate that if women have access to the LNG-IUS in this time period, most will continue use for at least 12 months and will have high levels of satisfaction. *Hypothesis:* Greater than 70% of women receiving the LNG-IUS as EC will have continued use and satisfaction.

It is our *expectation* that the information gained from completion of this aim will contribute to the growing body of literature describing continuation and satisfaction rates among different groups of LARC users.

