At the follow-up phone surveys, individual level information will be updated with new medical data including any new medical diagnosis, interval pregnancies since enrollment, and interval diagnosis of STIs. We will also assess fertility desires, recent and current contraceptive use, and recurrent emergency contraception utilization.

**Primary Outcome:** The **primary outcome** of this study is unintended pregnancy following emergency contraception at both 5 weeks and 6 months post-enrollment.

**Secondary Outcomes:** 1. Long acting reversible contraception (LARC) use at 6 and 12 months following method allocation will be evaluated. 2. Continuation and satisfaction among participants in the LNG-IUS arm.

**Potential Confounders:** There are a number of variables that make act as potential confounders. These variables will be tested for their association with the primary outcome and treatment assignment. Age is strongly associated with fertility. Other potential confounders include: race/ethnicity, socioeconomic status (measured by income or education level), history of sexually transmitted infection or pelvic inflammatory disease, previous or current contraceptive method. Given random assignment, we expect two arms will be balanced in terms of known and unknown confounding variables. However, if any imbalance is noted, we will control for possible confounders in our multivariable statistical analysis.

**Data Management:** Study staff located within the Division of Clinical Research will be responsible for data collection, entry, and management. Off-site staff will enroll participants remotely using the RedCap secure website. All telephone follow up surveys will be conducted by study staff of Washington University in St. Louis, School of Medicine. Data from telephone interviews will be entered using a secure web portal and stored on secure Washington University in St Louis Department of Obstetrics and Gynecology servers. All participants will be assigned a study identification number. This study I.D. will be used on all data forms and for all computer entries. Data entry will be completed using a custom software package (Illume™; DatStat Inc., Seattle, WA). The data manager will be responsible for data processing, validity checks, and communication with the team on data issues.

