**Secondary Aim2:** Long-acting reversible contraceptive (LARC) use (either an IUD or contraceptive implant) at 6 and 12 months will be compared between the two randomization groups and presented as frequencies. Women who become pregnant will be censored at that point, as well as those who stop the method because they desire pregnancy. Use of LARC and satisfaction in the LNG-IUD arm will be assessed as an ordinal variable and models with ordered logistic regression analysis.. We will compare women lost-to-follow up with the baseline sample to assess whether they vary on demographic factors or method type. If we detect non-random loss-to-follow-up, we will consider the impact on the interpretation of our results.

**Right to Withdraw or Removal from Study:** Participants are free to withdraw from this study at any time. The subject must inform the Investigator immediately if they intend to withdraw. To terminate the subject's participation in this study, they must contact PI listed on the informed consent form. They will be asked complete a brief end-of-study telephone interview. Their decision to participate in this study or to withdraw from this study will not influence the availability of their future medical care and will involve no penalty or loss of benefits to which they are otherwise entitled.

Study Principal Investigators, the FDA, or NEIRB (central IRB) can remove the subject from this study without their consent for any reason, including, but not limited to:

- a. Investigator judgment that any condition or circumstance may jeopardize their welfare or the integrity of the study.
- b. Participant fails to follow the instructions of the investigator(s).
- c. Side effects or complications experienced by the participant.
- d. If the study is stopped by the sponsor, Data Safety and Monitoring Board (DSMB), investigators, FDA, or NEIRB prior to completion.

**RISK MANAGEMENT:** All other known risks will be disclosed to the subject via the informed consent process.

Risks of either method of EC are outlined in the package insert and this protocol. There is also a risk of unintended pregnancy. Patients with a positive pregnancy test will be provided with options counseling.

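### Secondary Aim 2 asks how many women are both still using the LNG-IUS and satisfied with it, but the planned separate frequencies, with no rule for women who stopped, do not settle the >70% hypothesis

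*Combined protocol and SAP*

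**What the plan says.** The research question and the hypothesis put use and satisfaction together. Question 4 under INNOVATION asks whether women given the LNG-IUS as emergency contraception are "still using and satisfied with their method at 6 months and at 12 months". Secondary Aim 2 under APPROACH sets a single threshold: "Greater than 70% of women receiving the LNG-IUS as EC will have continued use and satisfaction". The same aim also uses the plural, since it is to "quantify the contraceptive continuation and satisfaction rates of the participants randomized to LNG-IUS".

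The outcome list in Evaluation/ Follow-Up gives only "Continuation and satisfaction among participants in the LNG-IUS arm", without a definition.

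The two analysis sections differ:

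- Statistical Approach & Data Analysis, Secondary Aim 2: "Both continuation and satisfaction will be assessed as dichotomous variables", followed by "Continuation and satisfaction (satisfied/ not satisfied) will be presented as frequencies and analyzed with Chi-square and logistic regression".
- Data Analysis/Statistical Methods, Secondary Aim 2: "Use of LARC and satisfaction in the LNG-IUD arm will be assessed as an ordinal variable", with ordered logistic regression. The same paragraph censors women who become pregnant and women who stop because they want a pregnancy. It does not say whether this censoring covers only the between-arm LARC comparison or satisfaction in the LNG-IUS arm as well.

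**The concern.** A woman who is still using the LNG-IUS and is satisfied with it is in one state. Two marginal frequencies do not give the proportion of women in that state unless it is known who was asked about satisfaction and how women who stopped were coded. The documents give neither. They name no joint variable, no denominator for satisfaction and no comparison with 70%.

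What is at stake is the only quantified hypothesis of this aim. Both components could be reported above 70% while fewer than 70% of the women who received the device are still using it and satisfied. A reader of the final report could not tell whether the question posed under INNOVATION had been answered.

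**Working it through.** **The plan's own figures.** The 70% threshold has no calculation behind it. The only computed figure is the total of 532, which concerns pregnancy. It can be approximately reproduced: 11% versus 2%, 3:1 allocation, 90% power, two-sided alpha 0.05 with continuity correction gives 108 UPA and 432 in total; 432 / 0.80 = 540, within 1.5% of 532. It does not bear on the present point except through arm size.

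**Inputs**

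- LNG-IUS arm: 399 (Power Analysis and Sample Size).
- Loss by 6 months: about 20% (same section), so 399 × 0.80 ≈ 319 women. No 12-month loss is given, so 319 is a 6-month figure only.
- Threshold: above 70% (APPROACH, Secondary Aim 2).
- Continuation *c* and satisfaction *s*: not given in the documents. The values below are assumptions chosen to show the range.

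**Case 1: satisfaction measured in continuers only.** Joint rate = *c* × *s*. Half-width = 1.96 × √[p(1 − p)/319].

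| c | s among continuers | joint rate | 95% interval, n = 319 |
|---|---|---|---|
| 75% | 75% | 0.75 × 0.75 = 56% | not needed |
| 75% | 85% | 0.75 × 0.85 = 64% | about ±5 points |
| 80% | 85% | 0.80 × 0.85 = 68% | about ±5 points |
| 85% | 85% | 0.85 × 0.85 = 72% | about ±5 points |

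In every row both components exceed 70%. In the first three the joint rate does not; in the last it does. Satisfaction among continuers needed for a joint rate of 70% is 0.70 / *c*: 93% at 75% continuation, 87.5% at 80% and 82% at 85%. If the two rates are equal, each must exceed √0.70 = 83.7%.

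**Case 2: satisfaction measured in all women, including those who stopped.** The joint rate lies between *c* + *s* − 1 and the smaller of *c* and *s*. With 75% and 75%, that is 0.75 + 0.75 − 1 = 50% up to 75%. With 85% and 85%, it is 70% to 85%. The marginal frequencies alone do not fix it.

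**Case 3: women who stopped coded as not satisfied, over the whole arm.** The satisfaction frequency then equals the joint rate and the gap disappears. The plan allows this coding but does not state it.

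**Effect of the censoring rule.** If censored women leave the denominator, the rate rises. At the 2% pregnancy rate assumed for the LNG-IUS in the sample size section, a joint rate of 68% over everyone, with none of those 2% a success, becomes 0.68 / 0.98 = 69.4%. The number who stop in order to conceive is not given, so no size can be put on that part.

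**Precision against 70%.** With 319 women, an exact one-sided 2.5% binomial test against 70% needs at least 240 joint successes (75.2%); with all 399 it needs 298 (74.7%). A joint endpoint can therefore be judged against the threshold with the numbers already planned.

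**The case against.** The strongest reply is that the aim is descriptive and two-part. It speaks of rates in the plural, its objective describes continued use and high satisfaction as two properties, and the outcome list and first analysis section follow suit. On that reading the threshold applies to each component, and reporting them separately is legitimate. This reading is tenable. It is not the natural reading of question 4 or of the hypothesis sentence, and since the choice can reverse the conclusion, it should be made in advance.

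Three stronger claims that a reader might infer are not supported:

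- *That satisfaction cannot be scored for women who stopped.* The 6- and 12-month calls are not restricted to current users, and the surveys collect recent and current contraceptive use, so these women are reachable and identifiable. They could rate the LNG-IUS or be coded not satisfied. What is missing is the rule.
- *That any scoring inflates satisfaction.* Case 3 does not. Nor do the documents show that the survey asks about whatever method a woman now uses, because the questionnaire is not included.
- *That the plan would declare the hypothesis met when it is false.* The plan contains no success rule at all: no test against 70%, and no statement that two frequencies above 70% suffice. It leaves that inference open but does not prescribe it.

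**Conclusion.** The point stands as under-specification with a concrete consequence. The hypothesis and the research question most naturally describe a joint rate over all women who received the LNG-IUS, and no planned output clearly delivers it. The two analysis sections also disagree on scale (dichotomous versus ordinal), and it is unclear how far the censoring reaches.

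The size depends on rates that the documents do not give. Across the assumed combinations with both components above 70%, the continuers-only joint rate runs from 56% to 72%, so the hypothesis may or may not hold. The argument does not depend on the sample size; the 319 used for precision applies at 6 months only.

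The importance is moderate. This is a one-arm descriptive secondary aim, and it does not touch the primary outcome, the randomised comparison or the total of 532. The change is worth making because it answers the trial's own question at almost no cost.

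**What to change.** In both Secondary Aim 2 analysis paragraphs:

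1. Add a joint binary endpoint at 6 and 12 months: LNG-IUS still in place and the woman satisfied with it. The denominator is all women who received the LNG-IUS, and women who have stopped count as non-successes.
2. Report it with a 95% confidence interval set against 70%.
3. State how women lost to follow-up are counted, and how women who become pregnant or stop because they want a pregnancy are counted, since the present censoring rule could remove them.
4. Reconcile the dichotomous and ordinal descriptions. If an ordinal satisfaction scale is collected, give the cut that defines satisfied.
5. Report continuation alone, and satisfaction among current users labelled as such, as supporting results.
6. Check that the satisfaction question refers to the LNG-IUS.

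The cost is analysis-plan wording and a check of one questionnaire item, with no added participants, visits or calls. The downside is that the headline rate will be no higher than either separate rate.

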### **Power Analysis and Sample Size**

Power analysis and Sample size calculation was performed with Epi-Info v 6.0.

**Sample Size:** With an alpha ( $\alpha$ ) = 0.05, power of 90%, and assuming unintended pregnancy rates (total 5 weeks through 6 months) of 11% for the oral UPA regimen and 2% for the LNG-IUS, and a 3:1 ratio of LNG-IUS allocation to UPA, we calculate our sample size to be 532 participants (399 LNG-IUS and 133 UPA). This accounts for approximately 20% loss to follow-up rate by 6 months. We chose a 3:1 ratio of LNG-IUS to UPA to allow for a more precise estimate of immediate failure rates of the LNG-IUS group.

### **Data Analysis/Statistical Methods:**

**Preliminary Analysis:** Descriptive analyses will include comparison of the baseline characteristics of participants in the two treatment arms. Continuous variables will be summarized using means, medians, and standard deviations. Categorical variables will be presented as frequencies. Continuous variables that are normally distributed will be analyzed with Students t-test, and nonparametric tests will be used for those that are not normally distributed. Chi-square and Fisher's exact tests will be used to analyze categorical variables.

**Primary Aim:** Observed pregnancies at 5-6 weeks and at 6 months in the LNG-IUD group will be compared to those in the oral UPA group. The analysis population is enrolled women who complete 5-6-week and 6 month follow-up. "Modified" intent to treat analysis will be used. Pregnancies will be presented as frequencies and chi-square tests will be used for analysis. We expect the two groups to be balanced on important confounding variables such as menstrual cycle day at the time of unprotected intercourse. However, if there are significant imbalances, stratified or multivariable analysis will be performed. Pregnancies at 5-6 weeks and 6 months will be compared by intervention arm with Kaplan-Meier estimates, using dating from last menstrual period time. Logistic regression will be used to control for confounding (if necessary) using the dichotomous outcome of pregnancy (yes/no) at each time point.

**Secondary Aim1:** Descriptive analyses will be used to compare demographic characteristics of participants who screen eligible, but decline to participate and those who enroll in the study. Reasons for declining participation will also be collected and qualitatively evaluated for recurrent themes.

**Secondary Aim2:** Long-acting reversible contraceptive (LARC) use (either an IUD or contraceptive implant) at 6 and 12 months will be compared between the two randomization groups and presented as frequencies. Women who become pregnant will be censored at that point, as well as those who stop the method because they desire pregnancy. Use of LARC and satisfaction in the LNG-IUD arm will be assessed as an ordinal variable and models with ordered logistic regression analysis.. We will compare women lost-to-follow up with the baseline sample to assess whether they vary on demographic factors or method type. If we detect non-random loss-to-follow-up, we will consider the impact on the interpretation of our results.

**Right to Withdraw or Removal from Study:** Participants are free to withdraw from this study at any time. The subject must inform the Investigator immediately if they intend to withdraw. To terminate the subject's participation in this study, they must contact PI listed on the informed consent form. They will be asked complete a brief end-of-study telephone interview. Their decision to participate in this study or to withdraw from this study will not influence the availability of their future medical care and will involve no penalty or loss of benefits to which they are otherwise entitled.

Study Principal Investigators, the FDA, or NEIRB (central IRB) can remove the subject from this study without their consent for any reason, including, but not limited to:

- a. Investigator judgment that any condition or circumstance may jeopardize their welfare or the integrity of the study.
- b. Participant fails to follow the instructions of the investigator(s).
- c. Side effects or complications experienced by the participant.
- d. If the study is stopped by the sponsor, Data Safety and Monitoring Board (DSMB), investigators, FDA, or NEIRB prior to completion.

**RISK MANAGEMENT:** All other known risks will be disclosed to the subject via the informed consent process.

Risks of either method of EC are outlined in the package insert and this protocol. There is also a risk of unintended pregnancy. Patients with a positive pregnancy test will be provided with options counseling.

**ADVERSE REACTIONS:** There are few side effects of UPA and LNG-IUS. These are listed in the protocol and informed consent form. Most side effects resolve spontaneously. Anticipated events means reactions to treatment previously observed that may require medical intervention but are not serious in nature.

All adverse events that occur will be recorded in the Source Documents. Adverse events should be captured in the medical history.

Adverse Events occurring will be captured and followed until the condition resolves, stabilizes, or is otherwise explained, or the subject is lost to follow-up. Subjects will be instructed that they may contact one of the Principal Investigator at any time throughout the course of the study.

The Investigator will review each event and assess its relationship to method of EC (not related, unlikely, possible, probable, and highly probable). The following definitions will be used for rating relationship to the treatments or investigational device:

- Not related – The event is clearly related to other factors such as the subject's clinical state, therapeutic interventions, or concomitant medications administered to the subject.
- Unlikely – The event was most likely produced by other factors such as the subject's clinical state, therapeutic interventions, or a concomitant medication administered to the subject; and does not follow a known response pattern to the investigational device.
- Possible – The event follows a reasonable temporal sequence from the time of investigational device administration; and/or follows a known response pattern to the study treatments; but could have been produced by other factors such as the subject's clinical state, therapeutic interventions, or concomitant medications administered to the subject.
- Probable – The event follows a reasonable temporal sequence from the time of investigational device administration; and follows a known response pattern to the investigational device; and cannot be reasonably explained by other factors such as the subject's clinical state, therapeutic interventions, or concomitant medications administered to the subject.
- Highly Probable – The event follows a reasonable temporal sequence from the time of investigational device administration; and follows a known response pattern to the investigational device; and cannot be reasonably explained by other factors such as the subject's clinical state, therapeutic interventions, or concomitant medications administered to the subject; and either occurs immediately following investigational device administration, or improves on stopping the investigational device, or reappears on repeat exposure, or there is a positive reaction at the treatment site.

Each adverse event reported will be graded on a 3-point severity scale. The following definitions for rating severity will be used:

- Mild – easily tolerated, causing minimal discomfort, and not interfering with normal everyday activities.
- Moderate – sufficiently discomforting to interfere with normal everyday activities.
- Severe – incapacitating and/or preventing normal everyday activities.

**A Serious Adverse Event** is any adverse device experience that results in any of the following outcomes: death, a life-threatening adverse device experience, in-patient hospitalization or prolongation of hospitalization, a persistent or significant disability/incapacity, or a congenital anomaly/birth defect. Important medical events that may or may not result in death, be life-threatening, or require hospitalization may be considered a serious adverse device experience when, based upon appropriate medical judgment, they may jeopardize the subject or subject may require medical or surgical intervention to prevent one of the outcomes listed in this definition

If any of the above adverse events are serious as defined by the FDA Code of Federal Regulations (CFR), Title 21, special procedures will be followed. All serious adverse events will be reported within 24 hours of acknowledgment to the Medical Monitor whether or not the serious events are deemed treatment-related. All serious event reporting will adhere to 21 CFR part 812 and the IRB will be notified accordingly.

Adverse events, whether serious or non-serious, will be followed until the condition is resolved, stabilized, or otherwise explained, or the subject is lost to follow-up. Adverse events will be captured up to one week after a subject completes the study and where appropriate, medical tests and examinations will be performed to document the resolution of event(s).

Outcomes may be classified as resolved, improved, unchanged, worse, fatal, or unknown (lost to follow-up). Following the resolution of any study-associated adverse events there will be no further adverse event reports for that subject.

**PROTOCOL DEVIATIONS:** No deviations from this protocol will be permitted, except in a medical emergency, without the approval of the Coordinating Center/Sponsor. Any amendment to this study will be discussed by the Investigators and the Coordinating Center. If agreement is reached concerning the need for modification, this will be made in a formal amendment to the protocol. All requests for protocol deviations must be approved by the IRB. If a deviation occurs, the Investigator must inform the Sponsor and IRB in writing within 10 days.

**DATA COLLECTION AND MONITORING:** The coordinating center (WashU/sponsor) will train all investigative sites. The sponsor will also monitor the site at various intervals and upon request expects to receive intermediate results by fax following each visit to evaluate treatment progress in accordance with the sponsor's monitoring procedures and guidelines. Case Report Forms and Investigator Binders will be reviewed for current data. The sponsor will collect data at the end of the follow-up period. The sponsor will list the study on clinicaltrials.gov as required by FDA regulations.

**CONFIDENTIALITY AND DISCLOSURE OF MEDICAL INFORMATION:** As part of this study the Investigator and the team at each research facility will keep records of subject participation in the study. These study records will include personal information that the subjects provide including age, sex, etc., the results of the study, information about response to treatments, and other medical information relating to participation in the study. Under federal law the study records cannot be used or disclosed by the research Investigator for research purposes unless subjects sign the informed consent authorization.

The sponsor and its consultants will analyze and evaluate study results and information and may report them to the U.S. Food and Drug Administration (the FDA) or other regulatory agencies in the United States. Study records will be assigned a code number by the study team and the subject will ordinarily not be identified by name in the study records that are sent to the Sponsor and its consultants. However, The Sponsor and its consultants will have the right to see the complete study records.

The research facility will review and use the study records for purposes of this study. De-identified data sets will also be shared with potential investors and others related to the business of the Sponsor. However, no identifiers will be shared with these third parties. They will keep the subject identity confidential and, except for the disclosures described above, will not disclose the study records to other parties unless disclosure is required by law. Once the research facility discloses information in the study records or medical records to the Sponsor or its consultants, the information will no longer be protected by federal law. Because of the need to release information to these parties, absolute confidentiality cannot be guaranteed. However, the Sponsor and its consultants will only use the information for purposes of the study and will not disclose the study records to parties other than the FDA and similar government agencies, unless disclosure is required by law. If reports or articles are written about the study, subjects will not be identified by name or other identifier.

**CLINICAL RESEARCH CONDUCT:** The study will be conducted in accordance with the protocol, International Conference on Harmonization (ICH) GCP guidelines, applicable regulations and guidelines governing clinical study conduct and ethical principles that have their origin in the Declaration of Helsinki. The investigators ensure that the study is conducted in accordance with the provisions as stated in the FDA regulations and complies with the applicable local or regional regulatory requirements.

**INFORMED CONSENT:** All participants will be introduced to the study and will be screened for eligibility based on above stated inclusion/exclusion criteria. If interested and eligible, potential participants will be given an informed consent form to read and review. Research personnel will then explain the study to the potential participant, outline key risks, benefits, and alternatives (including not participating), and then have participants signed the informed consent form (ICF). A copy of the ICF will be given to the participant, and a copy will be kept in the participants research file.

**REPORTING FOR THE STUDY:** A study summary report will be generated. It will include a description of the clinical conduct of the study and results, and the statistical analysis described in the data analysis section of this protocol. We anticipate that the results of this investigation will be submitted for publication in peer-reviewed journals.

**RESPONSIBILITY OF THE INVESTIGATOR:** The Investigator is responsible for ensuring that the clinical study is performed in accordance with the Declaration of Helsinki (revised version of Edinburgh, Scotland, 2000 including notes of clarification, Washington, 2002 and Tokyo, 2004) and FDA Good Clinical Practice Regulations (21 CFR parts 50, 56, and 812). Investigators will supply information to the sponsor such that the sponsor can comply with the Financial Disclosure Rules (21 CFR Part 54).

**INSTITUTIONAL REVIEW BOARD:** This protocol, informed consent forms, and any amendments to the protocol will be reviewed by the appropriate Institutional Review Board prior to initiation. The study will not be initiated without the approval from the Institutional Review Board.

**TERMINATION OF STUDY:** The Coordinating Center/Sponsor, Investigators, FDA, and NEIRB reserve the right to discontinue this study for administrative reasons at any time. Coordinating Center/Sponsor, Investigators, FDA, and NEIRB reserve the right to discontinue the study for safety reasons at any time.

**STUDY RECORDS:** All records and documents pertaining to the study will be maintained in appropriate permanent files as per the ICH guidelines for Essential Documents for the Conduct of a Clinical Trial and 21 CFR 11, and will be available for inspection by the Sponsor, Sponsor designee, or the Food and Drug Administration at any time.

**CONFIDENTIALITY:** After the informed consent has been signed, each subject will be entered on a screening/enrollment log, which will be kept with the study records. Once a subject is consented, a unique subject identification number will be assigned. No two subjects will have the same subject identification number. This subject identification number will identify the subject throughout the study and will be used for all source documents, and Data Collection Forms. The subject identification number will be held confidential so

far as permitted by law. Investigative site staff, the Sponsor or its designee, and, under certain circumstances, the FDA and Institutional Review Board (IRB) will be able to inspect and have access to the subject identification number and the confidential data that it links to. Any publication or presentation of data will not contain any identifiable subject information.

**DATA SECURITY:** To ensure the privacy and confidentiality of data for this protocol, the data will be stored on a restricted access location on a WashU server. Access to the project directory containing the data will be limited to the investigators and research staff. Information about data security awareness is promoted through user training and education, supplemented by policies and procedures. Password protection will be used for all transactions that allow viewing, editing, and analysis of data, or that provide access to data fields derived from the original source documents.

